Potential participants will be identified from digital review of the HUP operating room schedule based on current procedural terminology (CPT) codes 51590, 51595, 51596, 51597 or others that may be used to encode radical cystectomy. OR schedules will be reviewed for the coming two months by the research coordinator in conjunction with clinical staff. All patients scheduled for cystectomy will have their charts reviewed for eligibility. After being scheduled for cystectomy, patients are usually seen at a separate pre-admission testing (PAT) appointment and/or an appointment for stoma marking. Scheduled patients will be approached at the conclusion of one of these visits for recruitment by the study coordinator. For the small number of patients who have neither of these visits preoperatively, the study coordinator will initiate contact over the phone, consent will be obtained, the device will be mailed to the participant's home, Way to Health staff or the study coordinator will assist the patient in set up of the device, the consent documents will be signed in the preoperative holding area.

5. Early Withdrawal of Subjects:

Participants may choose to withdraw by simply ceasing to submit ambulation data. Participants will agree that all data submitted to the Way to Health (WTH) will be retained and may be used as part of the study. However participants may stop submitting new data at any time. If a participant fails to submit data for 24 hours while hospitalized, he or she will be approached in the hospital by the research coordinator who can help resolve technical problems, answer questions, and obtain ongoing consent or register the participant's withdrawal. If a patient fails to submit data for 24 hours between the time when they begin submitting data preoperatively and the end of the 30 day post-operative period, the research coordinator will contact the patient by phone and carry out the same process of troubleshooting or registering withdrawal.

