The main scenarios that might prompt early withdrawal are: 1) the patient voluntarily withdraws because he or she finds data tracking and submission too cumbersome or 2) the patient becomes incapable of submitting further data. There are no safety concerns that would necessitate study withdrawal. In the first scenario, the patient can simply cease reporting/recording data as above and sacrifice any further financial awards that might have been earned. If the second scenario occurs in the hospital, research staff will continue to submit data on the patient's behalf unless he or she expresses an objection. If the second scenario occurs after discharge, the participant or research staff may arrange for assistance from friends/family in submitting data. If such assistance is not possible or not desired by the participant, the participant will be withdrawn from the study.

6. Vulnerable Populations:

Children, pregnant women, fetuses, neonates, or prisoners are not included in this research study

7. Populations vulnerable to undue influence or coercion:

This study is unlikely to involve populations considered to be vulnerable to undue influence, including children, prisoners, pregnant women, mentally disabled persons, or employees or students of Penn. It may involve economically or educationally disadvantaged persons inasmuch as these populations are part of the usual patient population seen in our clinic. Since recruitment and education will be performed in one-on-one sessions, education regarding the study and its goals can be tailored to the appropriate learning level and style. Financial incentives are nominal and not expected to unduly influence economically disadvantaged participants.

STUDY DESIGN:

In this application, we propose a randomized controlled trial to test the hypothesis that small financial incentives can be used to increase post-operative ambulation. The randomized controlled trial design is necessary to demonstrate a causal relationship between the intervention (provision of financial incentives) and the outcome (increased ambulation). This design will also provide preliminary data (e.g. effect sizes, feasibility) needed to design larger trials that will determine whether increases in ambulation produced by financial incentives can be translated into decreases in clinically relevant outcomes such as post-operative complications, readmissions, and functional decline in patients undergoing major abdominal surgery.

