Subjects will be assigned to groups using simple balanced randomization. Upon enrollment in Way To Health, patients will be automatically randomized into "financial incentives" and "control" arms by an off-site computerized randomization system which is part of the WTH platform.

4. Administration of Surveys and/or Process:

Step count data will be recorded and uploaded independently by participants after initial instruction by the research coordinator. Before and after hospitalization, the research coordinator will ensure that patients are successfully uploading data and will be available to address issues that arise.

Questionnaires will be administered via the Way To Health platform. At the specified time points in the study (initial enrollment, immediately prior to discharge from the hospital, 30 days post-operative, and 90 days post-operative) the patient will be prompted to log in to the platform and fill out the questionnaire. Responses will be automatically recorded to the secure database.

Patients will also be contacted by phone at 30 days and 90 days by the research coordinator to screen for complications that would not be present in the University of Pennsylvania Health System (UPHS) electronic medical record (EMR).

5. Data Management:

Data will be collected principally through the Way to Health platform, which is a web-based platform designed by the University of Pennsylvania Center for Health Incentives and Behavioral Economics specifically for the purpose of testing behavioral interventions such as ours in an academic research setting. This platform has already been used in a number of similar IRB-approved randomized trials at the University of Pennsylvania.

All data not stored on WTH will be stored on hospital or university-owned computers or on encrypted storage drives. Data access will be granted only as needed to a small number of researchers who have completed the appropriate training as mandated by the University of Pennsylvania.

Upon completion of the study, data collection sites will be taken down and data stores disconnected from live webservers. Data will be stored on research computers for a period of 5 years, after it will be stored entirely on encrypted archival drives if no follow-up projects have been initiated.

6. Subject Follow-up:

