Participants enrolled in the data-collection phase of the study will be required to upload step count data daily to the Way to Health Website. Upload rates will be monitored and participants who fail to upload data for 24 hours will be contacted via their preferred contact phone number listed in the electronic medical record. The research coordinator will attempt to reach the participant daily for 3 days by phone, email, and the MyPennMedicine secure messaging service. If there is no response, the participant will be considered to have declined further participation. A final attempt will be made to contact the participant for the study conclusion interview. Regardless of participation status at the study conclusion, a check for all earned funds will be mailed to the study participant at the conclusion of the 30 day trial period. If participants stop uploading data daily but it can be confirmed that they are continuing to use the Zip device, arrangements may be made to upload the data for the study period in batch within 10 days of the conclusion of the study and allocate financial rewards according to the data collected.

STUDY PROCEDURES:

1. Detailed Description:

Participants will be enrolled on a rolling basis as they are identified. The following describes the sequence of steps for each participant

1. A potential participant is scheduled for radical cystectomy by the clinical staff. The surgical case is entered into the University of Pennsylvania Health System's electronic medical record by a Division of Urology surgery scheduler.
2. The research coordinator, with the assistance of clinical staff, reviews the surgery schedule on a weekly basis to detect patients who have been scheduled for radical cystectomy. Clinical staff are asked to alert the research coordinator if a patient is scheduled for cystectomy with a short lead time prior to the procedure. When a new case is scheduled, the coordinator reviews the patient's chart for eligibility.

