This study does not involve the analysis of existing data, blood, or tissue specimens. It will involve review of the patient's University of Pennsylvania Health System electronic medical record at several points in the study. After the patient is scheduled for cystectomy, the record will undergo screening for eligibility. No data will be abstracted from the record at this point. After enrollment the chart will be reviewed again for demographic information and past medical history which will be abstracted into the research database. It may also be reviewed as necessary during the course of the study to ensure ongoing safety of participants. Finally, the record will be reviewed at the conclusion of the study to assess for complications. In the case of missing or contradictory data, the electronic medical record may be referenced to ensure the quality of collected data after the end of the study, but these reviews shall not substantially expand the scope of the data collected beyond demographic information, vitals, and past medical history present at time of study initiation.

3. Genetic Testing:

Not applicable

4. Use of Deception:

Not applicable.

5. Statistical Analysis:

We will use generalized estimating equations with participant random effects and fixed effects for time to determine the association between financial incentives and 1) achieving step goals, 2) mean number of steps taken, 3) complications, ED visits and hospital readmissions, and 4) functional decline.

As a pilot study, the proposed research will provide preliminary data (e.g. effect sizes, feasibility) needed to design larger trials that will determine the effectiveness of financial incentives to increase ambulation on decreasing post-operative complications, readmissions, and functional decline. This study was therefore not powered to detect a statistically significant difference between the groups.

RISK/BENEFIT ASSESSMENT:

1. Risks:

The primary risk is that the interventions taken in this trial result in behavioral changes that are actually deleterious to patient recovery. In theory, increased ambulation may lead to increased falls, increased pain, herniation or other wound

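### Ending step uploads and leaving outcome follow-up share one status, so the SHAQ and out-of-system events may be selectively missing in sicker patients

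*Combined protocol and SAP*

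**What the plan says.** Three rules tie the end of step uploading to leaving the study.

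- Early Withdrawal of Subjects (Characteristics of the Study Population, item 5) makes silence a way out: "Participants may choose to withdraw by simply ceasing to submit ambulation data".
- The same section covers a patient who becomes unable to upload after discharge. Help may be found ("the participant or research staff may arrange for assistance from friends/family in submitting data"), but otherwise: "If such assistance is not possible or not desired by the participant, the participant will be withdrawn from the study".
- Subject Follow-up (Methods, item 6) covers 24 hours without data followed by three days of unanswered phone, email and portal contact: "If there is no response, the participant will be considered to have declined further participation". It adds: "A final attempt will be made to contact the participant for the study conclusion interview".

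Other provisions limit the damage.

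- Inpatient incapacity is handled differently: "If the second scenario occurs in the hospital, research staff will continue to submit data", unless the patient objects.
- Administration of Surveys (Methods, item 4) schedules calls: "Patients will also be contacted by phone at 30 days and 90 days by the research coordinator to screen for complications". Their stated purpose is to find complications that the UPHS record would not show.
- Detailed Description (Study Procedures, item 1, step 11) has the coordinator obtain outside records after the day-31 contact and chase incomplete questionnaires.
- Data Collection (Study Procedures, item 2) plans a chart review: "Finally, the record will be reviewed at the conclusion of the study to assess for complications".

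None of the calls, record requests or chart reviews is conditional on uploading. None is said to continue after withdrawal.

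**The concern.** Two of the three secondary outcomes, the morbidity composite and functional decline on the SHAQ, can be measured without a single step count. The rules nonetheless let the end of step data end participation as a whole. The triggers are incapacity and silence, and serious illness can cause both. A patient admitted to an outside hospital after discharge, unable to upload or reply for several days, could be removed because of the event that the composite is meant to count.

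Loss of this kind depends on the outcome. The Statistical Analysis section names generalized estimating equations but no analysis set and no missing-data method. Fitting such a model to the available data does not correct outcome-dependent loss. Since the pilot exists to supply effect sizes for later trials, a distorted event rate or contrast would carry forward into their design.

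**Working it through.** **1. Which situations end participation**

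- Incapable in hospital: no withdrawal; staff upload.
- Incapable after discharge, with a helper: no withdrawal; friends or family upload.
- Incapable after discharge, help impossible or not wanted: withdrawn from the study.
- Silent through three days of attempts: deemed to have declined; one closing attempt. Batch upload is possible later if device use is confirmed.
- Chooses to stop uploading: counts as withdrawal.

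The exposure is in the last three.

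**2. What each outcome needs**

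- SHAQ: the patient's own answers at 30 and 90 days, by platform or around the calls. No chart substitute exists, so this is the most exposed outcome.
- Events outside UPHS: a reached patient, because outside records follow from the coordinator's inquiry. This is the second most exposed.
- Events inside UPHS: chart review, which can find them without the patient.

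One closing attempt does not replace two scheduled contacts. The separate record check for missing or contradictory data is confined to baseline-type information.

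**3. The plan's own figure**

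There is no power calculation to reproduce. The figure n = 46 is half of eligible patients: 0.5 × 75 = 37.5 and 0.5 × 100 = 50, so 46 lies in range and implies 46 / 0.5 = 92 eligible. It merges recruitment with retention, so no loss rate follows from it.

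**4. Illustration for the composite (all inputs assumed)**

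Let p be the true rate, L the share lost and w the event rate in those lost. The observed rate among those retained is (p − L·w) / (1 − L). Take p = 0.40 in both arms, L = 0.25 in controls and 0.10 in the incentive arm.

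- w = 0.5: controls (0.40 − 0.125)/0.75 = 36.7%; incentive (0.40 − 0.05)/0.90 = 38.9%; difference 2.2 points.
- w = 0.7: controls (0.40 − 0.175)/0.75 = 30.0%; incentive (0.40 − 0.07)/0.90 = 36.7%; difference 6.7 points.
- w = 0.9: controls (0.40 − 0.225)/0.75 = 23.3%; incentive (0.40 − 0.09)/0.90 = 34.4%; difference 11.1 points.

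Each is a false excess in the incentive arm. If the incentive arm lost more instead, the sign would reverse. With L = 0.20 in both arms and w = 0.7, both observed rates are (0.40 − 0.14)/0.80 = 32.5%: no false difference under the null, but the rate is understated by 7.5 points.

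**5. A second parameterization**

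Take the Background's 30% major-complication rate and an assumed 20% overall loss, with loss r times as likely in patients with events. Then q = 0.20/(0.30r + 0.70), and the observed rate is 0.30(1 − r·q)/0.80. This gives 30.0% for r = 1, 26.0% for r = 2 and 23.4% for r = 3.

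**6. Bounds without a model**

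With 23 per arm (46 split equally), three missing outcomes per arm leave the arm difference undetermined over 2 × 3/23 = 26 points.

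**The case against.** A reader might infer that these outcomes are simply lost once uploading stops. The documents do not say that. The chart review, both calls and the retrieval of outside records carry no upload condition, and the closing attempt is aimed at the very people deemed to have declined. This stands: the supportable statement is that the outcomes may be missing selectively, because continued follow-up is never stated for patients whom the plan calls withdrawn.

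A reader might also infer that becoming too ill to upload means withdrawal. It does so only after discharge, and only where help is impossible or unwanted. Applying the Background's event rates to 46 participants would not size the problem either. That yields expected events, which may overlap and may occur during the index stay, and not expected withdrawals.

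The argument for unequal loss is weaker than it first looks. Under Compensation, both arms can earn 75 dollars for 27 recorded days, more than the maximum of 30 × 1.50 = 45 dollars in daily payments. A patient too ill to meet goals earns no daily payment in either arm. Still, only the incentive arm has daily payments and the lottery, so a difference remains possible.

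Finally, the pilot is unpowered and morbidity is secondary. At 40% with 23 per arm, the standard error of the difference is √(2 × 0.40 × 0.60/23) = 14.4 points, so the middle illustration of 6.7 points is under half of it. That limits the consequence but does not justify an avoidable bias.

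**Conclusion.** The concern holds in this limited form, with moderate confidence. The rules for incapacity after discharge and for non-response are stated rules, and following them can end SHAQ collection and weaken detection of non-UPHS events for reasons plausibly tied to those outcomes. UPHS events and inpatient incapacity are largely protected.

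Neither the amount of loss nor any difference between arms can be derived from the documents. The 2.2 to 11.1 points rest wholly on the assumed 40% rate, the 25% and 10% losses and the event rates in those lost; with equal loss there is no bias in the contrast under the null, only an understated rate. The consent pages are not in the reviewed text, so consent may already separate step collection from follow-up. This is a cheap improvement.

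**What to change.** - **Early Withdrawal, incapacity after discharge:** replace withdrawal from the study with an end to step-count collection only.
- **Subject Follow-up, non-response:** classify the participant as having stopped step upload. Keep the ordinary day-30 and day-90 contacts, the SHAQ and the end-of-study chart review.
- **Early Withdrawal, registering withdrawal:** keep the easy way out, but have the coordinator ask whether the participant is stopping steps only or all follow-up. Honour a refusal of either. Record the date and reason by arm.
- **Proxy information:** a family member may report hospitalizations and ED visits; the SHAQ stays self-reported.

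The cost is a few extra call attempts and a wording change to the protocol, and to the consent form if it does not already draw this distinction. The calls and chart review are already planned, and the sample size does not change.

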The target population is adults undergoing radical cystectomy (RC) at the Hospital of the University of Pennsylvania (HUP). 75-100 patients undergo RC at HUP each year. We anticipate recruiting and retaining 50% of eligible patients (n=46) over a one-year enrollment period. Each patient will be followed for 30 days post-operatively with the option for patients to continue submitting data for up to 90 days after their procedure. We anticipate initiating recruitment in July of 2016.

2. Key Inclusion Criteria:

1. Patient is at least 21 years old. – This excludes pediatric patients who would certainly not be representative of the general cystectomy population.
2. Patient is planned to undergo radical cystectomy at the Hospital of the University of Pennsylvania. – This is the population to which we have access for recruiting purposes.
3. Patient is ambulatory with baseline ECOG performance status less than or equal to 2. – This excludes patients for whom step counts would not be relevant or a good measure of daily activity.

3. Key Exclusion Criteria:

1. Patient is non-ambulatory or use of Fitbit to monitor activity is otherwise impossible or impractical. – See inclusion criterion #3 above.
2. Patient has a preoperative ECOG performance status of 3 or greater. – See inclusion criterion #3 above.
3. Patient knows *a priori* that he or she will be unwilling or unable to use a mobile device and online tool to upload activity data.
4. Patient is incapable of consenting for him or herself prior to surgery – Because participation in this trial involves ongoing effort on the part of the subject, we exclude patients who are incapable of consenting for themselves at baseline.
5. Patient is unable to collect step count data for at least 3 days preoperatively – Because step count goals are determined based on preoperative status, we exclude patients for whom we have insufficient preoperative step count data.

4. Subject Recruitment and Screening:

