Investigators, statisticians, and clinical staff will be blinded to participant group assignments. The research coordinator, however, will be unblinded by necessity. Participants similarly must be unblinded to their incentive structure, however they will not be told the incentive structure of the other group, nor whether their group is designated the treatment or control group.

Implementation of this project will occur in four phases.

- Phase 1: Preparation. (Study Approval – July 2016). During this phase, a research coordinator will be hired, equipment will be purchased, and all systems will be tested to ensure basic functionality prior to recruitment of the first participant.
- Phase 2: Recruitment. (July 2016 – June 2017). This phase describes the up to 10 month recruitment period during which patients will be screened and enrolled on a rolling basis into the trial.
- Phase 3: Data acquisition. (Enrollment – 30 days post-operative). This phase, which will overlap with phase 2 and start at a different time for each participant, describes the period for each participant in which they are enrolled and actively encouraged to submit data via the Way to Health platform and via interviews by the research coordinator. This phase bounds the total time commitment for any single study participant.
- Phase 4: Optional additional data submission and final survey (31 days post-operative to 90 days post-operative). This phase describes a period where patients will be allowed to continue to access the Way to Health platform and submit data should they choose to do so. No financial rewards or active encouragement will take place during this time. A final survey will be administered at the conclusion of this 90 day period to capture mid-term outcomes and complications.
- Phase 5: Analysis and Publication (Enrollment completion – December 2017). Final analysis of all acquired data is projected to be complete and ready for submission for publication by the end of 2017.

METHODS:

1. Study Instruments:

- Beginning shortly before the planned surgery and continuing for 30 days after date of surgery, all participants will use Fitbit Zips to measure daily step counts. Patients will have the option of submitting up to 90 days of post-operative data. Post-operative ambulation has been repeatedly demonstrated to be beneficial to recovery by a number of different metrics, and the Zip device has been shown to be an accurate measure of step counts.^{4-10,31}

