Research staff will include the two Principal Investigators, [name] and [name], at least one resident physician, and at least one research coordinator. The last of these will be hired as 0.75 of a full time employee. All project members in this small team will be intimately involved in the design and implementation of protocols. The Co-PIs will be jointly responsible for overseeing project planning, strategy, and operations. [name] will be the clinical operations leader at UPHS and will be primarily responsible for resolving clinical questions about eligibility for study participation and developing effective communications with participants. [name] will hold primary responsibility for coordination of the research activities with Way To Health, designing the structure of the financial incentives, and overseeing data analysis. Both co-PIs have completed fellowships including at least 1 year of dedicated research time and have earned advanced degrees in the design and implementation of clinical studies. Dedicated research space is available at the offices of the Division of Urology in the Perelman Center for Advanced Medicine, which will be sufficient to provide working space for dedicated research personnel and to provide storage space for the Zip devices, documentation, and a small amount of peripheral equipment that may need to be purchased.

The target population is adults undergoing radical cystectomy (RC) at the Hospital of the University of Pennsylvania (HUP). 75-100 patients undergo RC at HUP each year. We anticipate recruiting and retaining 50% of eligible patients (n=46) over a one year enrollment period. Each patient will be followed for 30 days post-operatively with the option for patients to continue submitting data for up to 90 days after their procedure. We anticipate initiating recruitment in July of 2016.

REFERENCES:

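### Does describing recruitment as lasting up to 10 months undermine the anticipated 46 participants?

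*Combined protocol and SAP*

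**What the plan says.** The combined protocol and SAP gives the length of recruitment in three places.

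- **Characteristics of the Study Population, 1. Target Population and Accrual.** The site volume is given as "75-100 patients undergo RC at HUP each year", followed by "We anticipate recruiting and retaining 50% of eligible patients (n=46) over a one-year enrollment period". The start is "We anticipate initiating recruitment in July of 2016".
- **Resources Necessary for Human Research Protection.** The same paragraph appears again, with "We anticipate recruiting and retaining 50% of eligible patients (n=46) over a one year enrollment period".
- **Study Design, implementation phases.** The entry opens with "Phase 2: Recruitment. (July 2016 – June 2017", and its next sentence reads "This phase describes the up to 10 month recruitment period during which patients will be screened and enrolled".

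No section explains the 10 months or gives a separate sample size for it. Under Study Procedures, 5. Statistical Analysis, the plan says of the sample size: "This study was therefore not powered to detect a statistically significant difference between the groups".

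**The concern.** Ten months is not a year, and 46 is tied to a year. A team that closed recruitment at month 10 would expect to finish short of 46, whereas a team working to the calendar dates would not. The plan has no power calculation, so this accrual projection is the only basis it offers for the sample size. The pilot exists to supply effect sizes and feasibility data for later trials, and a smaller sample would make those estimates less precise.

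A second doubt is whether 46 is too optimistic even for a full year, since it sits towards the top of what the stated volume can deliver.

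**Working it through.** **Inputs.** Volume is 75 to 100 cystectomies a year, uptake is 50%, and the anticipated n is 46 over one year (Target Population and Accrual). The phase runs July 2016 to June 2017 and is also called up to 10 months (Study Design). The eligible fraction is not given, so every patient is counted as eligible, which favours accrual.

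**1. Reproduce the plan's figure.** Expected n = annual volume × 0.50 × months/12.

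- At 12 months: 75 × 0.50 = 37.5 and 100 × 0.50 = 50. The range contains 46.
- Volume implied by 46: 46/0.50 = 92 eligible a year, inside 75 to 100.
- Midpoint volume: 87.5 × 0.50 = 43.75, which is 2.25 below 46.

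The figure is consistent with its inputs over the period it is attached to, at the upper end of the range.

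**2. The same formula at 10 months.**

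| Volume a year | 12 months | 10 months | Months to reach 46 |
|---|---|---|---|
| 75 | 37.5 | 31.3 | 14.7 |
| 92 | 46.0 | 38.3 | 12.0 |
| 100 | 50.0 | 41.7 | 11.0 |

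Expecting 46 in 10 months would take 92 × 12/10 = 110.4 eligible patients a year, above the stated range. At 100 a year it would take an uptake of 46/83.3 = 55%. If accrual is Poisson (an assumption), the chance of at least 46 at 92 a year is about 0.13 in 10 months and 0.52 in 12.

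**3. What the dates allow.** They are given to the month only. From 1 July 2016 to 30 June 2017 is 364 days, or 364/30.4375 = 12.0 months. From 31 July to 1 June is 305 days, or 10.0 months. Twelve is the natural reading. Ten is possible, so the Phase 2 entry need not contradict itself, but it then still differs from one year elsewhere.

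**4. Effect on precision, holding volume fixed.** For illustration only, take a two-sample t interval with near-equal arms, not the planned model. The half-width in SD units is t(0.975, n−2) × √(1/n₁ + 1/n₂).

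- n = 46: 2.015 × √(2/23) = 0.594.
- n = 38: 2.028 × √(2/19) = 0.658.
- Ratio: 0.658/0.594 = 1.11, or 11% wider.

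At 100 a year (42 against 50) and at 75 a year (31 against 37) the widening is about 10%. Comparing 31 with 46 gives 24%, but that combines low volume with the shorter period and overstates what the wording alone could do.

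**5. Does anything else in the plan use the duration?**

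- Analysis: no power claim is made, and Data and Safety Monitoring plans no interim analysis.
- Timeline: enrollment to 30 June 2017, plus a lead-in of up to 2 weeks and 90 days of follow-up (14 + 90 = 104 days), ends about 12 October 2017. That is before the December 2017 date for analysis and publication.

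**The case for a change.** The best case for a change is that feasibility is one of the pilot's stated products, and accrual is normally judged against a fixed period and an expected count. At 92 eligible a year, 38 participants at month 10 is on course if enrollment runs for a year and 8 short if it stops there. The analysis phase is also timed from the end of enrollment, and correcting one phrase costs almost nothing.

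The mismatch itself stands, and the phrase that calls 10 months an upper limit does not soften it. The consequence does not follow, for two reasons. First, the plan sets no accrual threshold for judging feasibility, and the monthly rate is the same on either reading: 38.3/10 = 46/12 = 3.83 participants. Investigators will report the dates and numbers that occurred. Second, no section instructs the team to stop at month 10. The phase list is descriptive and loosely edited, since it announces four phases and then lists five.

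It can also be said that 46 should be given as a range of 37 to 50, because it needs 92 eligible patients out of at most 100 and so leaves room for only 8 exclusions. The figure is indeed on the hopeful side. It is worded as an anticipation and lies within its inputs, so asking for a range is a preference about presentation.

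**Conclusion.** The discrepancy is real but clerical. One descriptive phrase differs from the one-year period stated in the accrual paragraph and its repeat, and from the natural reading of the dates beside it. Were the 10 months taken literally, expected accrual at the implied 92 eligible a year would fall from 46 to about 38 (31 to 42 across the stated volumes), and an interval would be about 11% wider. Those figures assume 50% uptake, steady accrual and every patient eligible; the interval figure also assumes a simple two-arm comparison. The sensible reading is the dated year, on which 46 is consistent with the plan's own inputs. No test, power claim, interim look or later deadline depends on the choice, so no change to the plan is needed.
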